3 OBJECTIVES

3.1 Primary objective(s)

The primary objective of the study is to determine whether add-on therapy with ponesimod reduces relapse frequency as compared to placebo in subjects with active RMS who are treated with DMF (Tecfidera[®]).

3.2 Secondary objectives

- To assess the effect of add-on therapy with ponesimod vs placebo on disability accumulation and on other aspects of multiple sclerosis (MS) disease control in subjects with RMS who are treated with DMF (Tecfidera[®]);
- To assess the safety and tolerability of add-on therapy with ponesimod vs placebo in subjects with RMS who are treated with DMF (Tecfidera[®]).

4 CHANGES OR CLARIFICATIONS TO ANALYSES PLANNED IN THE STUDY PROTOCOL

4.1 Changes to the analyses planned in the study protocol

The early termination of the study has significant impact on the power of the study to detect differences, and some endpoints require a minimum time on study that is reached by very few subjects. As a synoptic CSR will be produced to report the study data, only key efficacy and safety data will be reported.

The following additional changes are also applied:

- In the study protocol section 6.1.2 (secondary efficacy endpoints), the derivation of the time to 12-week confirmed disability accumulation (CDA), states that “for the purpose of confirmation, only EDSS measured more than 30 days after the onset of a confirmed relapse will be used.”. Relapses with unspecified end date are considered resolved at 90 days post onset. SAP Section 5.4.2.1 clarifies that the cutoff used will be 90 days rather than 30 days in line with this definition.
- The study protocol states that the mean number of combined unique active lesions (CUALs) and T2 lesions will be estimated per subject per scan, from negative binomial models including the log of the number of scans as an offset variable. However, the number of T2 lesions is expected to increase with observation time, and as the premature EOT magnetic resonance imaging (MRI) scan can occur at any time, ‘number of MRI scans’ is not necessarily expected to be a good approximation of the observation time for T2. This also applies to CUALs as with MRI scans scheduled every 24 weeks, the CUAL count is expected to be mainly driven by new T2 lesions. Therefore, instead, the mean number of CUALs and T2 lesions will be estimated per subject per year, from negative binomial models including the log of time up to last MRI scan as an offset variable.

- The protocol defines the treatment-emergent period as up to 30 days following study drug discontinuation. This is updated in this SAP to up to 15 days following study drug discontinuation, in-line with the approach used for analysis across the ponesimod MS program.
- The protocol states that “All safety data will be included in listings, with flags for safety data not considered to be treatment-emergent.”. This approach will be reversed, i.e. the flags will be applied to treatment-emergent data points.
- The protocol states that “The lymphocyte count reversibility after EOT will be summarized by plotting the mean (and 95% CIs) change from baseline to EOT and change from baseline to EOS by treatment. A scatter plot will display the change from baseline to EOS versus the change from baseline to EOT on an individual subject level by study treatment.”. This analysis will not be performed as the change from EOT does not consider the relationship to baseline and can therefore be misleading.

4.2 Changes in the conduct of the study / data collection

A total of 5 global protocol amendments were conducted. The main reasons are described below.

Protocol version 2, 4 December 2015: Main reason for the amendment was to address comments received after Special Protocol Assessment (SPA) review by the US FDA. The main changes were introduction of a standardized procedure for reporting and confirming relapses (relapse assessment questionnaire), clarification of the process for EDSS and functional system (FS) assessment, modifications and clarifications to the primary efficacy analysis and definitions associated with the primary endpoint, modification of the inclusion/exclusion criteria in the context of the SAP procedure, and clarification on the data review process by the IDMC during the study.

Protocol version 3, 9 March 2016: Main reason for the amendment was to add further clarification to address the comments received during the US FDA’s review of the SPA.

Protocol version 4, 17 June 2016: Main reason for the amendment was to address the comments received during the Voluntary Harmonization Procedure review for this Clinical Trial Application in the EU. The main changes were the addition of a new section to describe the known and potential risks and benefits associated with the participation in the study, the introduction of the electronic self-rated version of the Columbia-Suicide Severity Rating Scale (eC-SSRS[®]) to monitor subjects for suicidal ideation or behavior during the study, the addition of further criteria to allow modification of treatment in case a subject experiences relapses/lack of efficacy during the study, and clarification that the hormonal methods of contraception are restricted to those which are associated with inhibition of ovulation. Additional changes were made to minimize the potential risks for subjects, to enhance subjects’ safety monitoring, and to alleviate the burden on subjects and sites.

Protocol version 5, 8 December 2016: Main reason for the amendment is to clarify that subjects will be re-consented to continue receiving study drug if they meet one of the following conditions: completed at least 48 weeks of treatment in the study and has had at least one confirmed relapse which occurred after 12 or more weeks of treatment, experienced two confirmed relapses while on study treatment, or experienced an event of 24-week CDA while on study treatment.

Protocol version 6, 21 December 2017: Main reason for the amendment is to make changes to inclusion criteria 6, which is modified to include the presence of at least one new or one unequivocally enlarging T2 lesion on MRI on a pre-randomization scan as an alternative criterion of disease activity, and also to include the presence of T1 gadolinium enhancing (Gd+) lesions observed on the pre-randomization MRI scan as an alternative criterion of disease activity.

Additional local amendments were also created.

4.3 Clarifications concerning endpoint definitions and related variables or statistical methods

The following clarifications are applied:

- Mean number of CUALs up to EOS is given in the protocol as secondary efficacy endpoint. It is also listed as an exploratory MRI endpoint. It is clarified here that it is considered to be a secondary endpoint.
- The derivation of the ‘HH’ and ‘HHH’ ranges for hemoglobin marked abnormalities were changed to better clarify how to derive pre-treatment assessments and post-treatment assessments when baseline is \leq upper limit of normal (ULN) [see Appendix C for details].

5 DEFINITIONS OF VARIABLES

This section provides the definitions and sources for all variables used in the analyses, including specifications for the derivations.

General recurrent definitions (e.g., study treatment start date, baseline, and EOS date) or unit conversions are described in Section 11.

5.1 Subject disposition

5.1.1 Screened subjects

A subject is considered screened if the subject has signed any informed consent (for the main study or the lymphocyte sub-study) and is assigned a subject number by the interactive response technology (IRT) provider. A screened subject is considered re-screened if a second screening visit date is documented in the electronic Case Report Form (eCRF). The same subject number is used in the case of re-screening.

5.1.2 Screening failures

A subject is considered a screening failure, if screened but not randomized into the study (as per the recording in the IRT system). Subjects screened more than once and subsequently randomized are not counted as screening failures.

The reason for not being randomized is documented on the randomization eCRF:

- Failure to meet randomization criteria (“Is subject eligible as per inclusion/exclusion criteria?” answered “No”)

OR

- “Subject withdrew consent” or “Other” (Reason provided following “Was the subject randomized?” answered with “No”)

If a subject at a screening attempt is not randomized but no reason for not being randomized is reported, the reason is categorized as ‘Unknown’. Two variables are derived to hold reason(s) for not being randomized:

- Reason for not being randomized at first attempt (not applicable [NAP], if subject randomized at first attempt; reason derived from first attempt, irrespective of existence and outcome of a second attempt)
- Reason for screening failure (NAP, if subject randomized; reason derived from first attempt if no second attempt, or from second attempt otherwise)

5.1.3 Subjects randomized

A subject is considered randomized if a randomization date and number are recorded in the IRT system.

5.1.4 Subjects treated

A subject is considered treated if they received at least one dose of study drug as documented in any study drug log eCRFs (see Section 5.3.1 for eCRFs involved).

5.1.5 Subject study treatment completion status

Due to the early termination of the study, no treatment completers as per protocol are expected as no subjects will have completed 156 weeks of treatment / 60 weeks of treatment following randomization of the last subject.

Subjects who complete study treatment up to study termination are defined as those meeting any of the following conditions:

- a record in the eCRF ‘Maintenance Ponesimod/Placebo’ form with reason for treatment end given as ‘Completed as per protocol’;
- reason ‘Sponsor decision’ with sub-reason ‘Study termination’ (for question ‘Study treatment stopped due to’) is reported on the eCRF form ‘Premature Discontinuation of Study Treatment’,
- the reason for treatment end is documented as ‘Study Closure Announcement by Sponsor’ on the eCRF ‘Up-titration Ponesimod/Placebo’ or ‘Maintenance Ponesimod/ Placebo’.

A subject is considered to have prematurely discontinued from the study treatment if:

- at least one reason (‘Study treatment stopped due to’) which is not ‘Sponsor decision’ with sub-reason ‘Study termination’ is reported on the eCRF form ‘Premature Discontinuation of Study Treatment’ and/or
- the reason for treatment end is documented as ‘Premature Permanent Discontinuation’ on the eCRF ‘Up-titration Ponesimod/Placebo’ or ‘Maintenance Ponesimod/ Placebo’.

The date of treatment discontinuation is the last date study drug was taken [defined in Section 5.3.1.1]. In case of a (partially) missing discontinuation date, the date is imputed with the EOS date as defined in Section 5.1.6, or with the upper limit of the partial date if prior to EOS.

Reasons for premature discontinuation from study treatment are documented on the ‘Premature Discontinuation of Study Treatment’ eCRF with the following possible answers: ‘Death’, ‘Lost to follow-up’, ‘Pre-specified study treatment discontinuation criteria’, ‘Subject decision’ (further split into ‘Adverse event’, ‘Lack of efficacy’, ‘No reason provided’, or ‘Other’), ‘Physician decision’ (further split into ‘Adverse event’, ‘Lack of efficacy’ or ‘Other’) or ‘Sponsor decision’ (sub-reason ‘Other’). Whenever ‘Other’ is selected, free text can be provided in addition. Both recorded levels for treatment discontinuation (e.g., ‘Subject decision’ as well as ‘Adverse event’), if pre-specified, are to be included in analyses, while any free text is not to be reported in tables, only listed. An additional category called ‘Reason not provided’ is defined for subjects where the reason is missing.

5.1.6 Subject study completion status

A subject is considered to have completed the study up to study termination if the corresponding entry on the ‘Study Discontinuation’ eCRF for question ‘Study stopped due to’ is answered with ‘Sponsor decision’ and corresponding specify field is answered with ‘Study termination’. These subjects are considered to have completed study up to study termination.

All subjects not completing the study up to the early termination of the study as defined above are considered to have prematurely discontinued the study.

The EOS date is defined as the ‘Date of Subject Decision’ (if reason for study discontinuation was ‘Subject Decision/Withdrawal of consent’), ‘Date of Physician Decision’ (if reason for study discontinuation was ‘Physician Decision’) collected on the ‘Study Discontinuation’ eCRF, or ‘Date of recorded last study visit / assessment’ (if reason for study discontinuation was ‘Sponsor Decision’), unless a subject is lost to follow-up or dies, in which case ‘Date of last successful contact’ from the Study Discontinuation eCRF or ‘Date of Death’ from Death eCRF are used. If missing, the last recorded visit date (i.e., the latest assessment date within any visit) is considered as the EOS date.

For subjects prematurely discontinuing the study, reasons for premature discontinuation from study are: ‘Death’, ‘Lost to follow-up’, ‘Subject decision/Withdrawal of consent’ (further split into ‘Adverse event’, ‘Lack of efficacy’, ‘No reason provided’ and ‘Other’), ‘Physician decision’ (further split into ‘Adverse event’, ‘Lack of efficacy’ and ‘Other’) or ‘Sponsor decision’ (‘Other’). Whenever ‘Other’ is selected, free text can be provided in addition. An additional category ‘Reason not provided’ is defined for subjects where the reason is missing.

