5.4.2 Secondary efficacy variables

5.4.2.1 Time to 12-week confirmed disability accumulation (CDA) up to EOS

Time to first 12-week CDA is defined as the time from start date of the first onset of 12-week CDA minus date of randomization + 1 in days. Subjects without 12-week CDA are censored, following the rules below. It is assessed from baseline up to EOS.

Assessing disability by EDSS

Disability as measured by EDSS is assessed in all subjects at screening, baseline, and thereafter at scheduled visits every 12 weeks until the end of study. Additional EDSS assessments for individual patients may be conducted between scheduled visits (i.e., during an MS relapse). The EDSS is a disability scale that ranges from 0 (normal) to 10.0 (death) in 0.5-point steps (1-point step from 0 to 1). It is based on standard neurological examination in conjunction with observations concerning ambulation. For analysis the overall EDSS score as reported by the investigator from the eCRF is considered (Field: ‘Expanded disability status scale’).

EDSS increase criteria for disability accumulation

The following criteria for an increase in EDSS in derivation of disability accumulation apply:

- Increase of at least 1.5 in EDSS for subjects with a baseline EDSS score of 0;
- Increase of at least 1.0 in EDSS for subjects with a baseline EDSS score of 1.0 to 5.0;
- Increase of at least 0.5 in EDSS for subjects with a baseline EDSS score ≥ 5.5 ;

where baseline EDSS is defined as the last available EDSS score prior to or on the date of randomization.

12-week CDA

A 12-week CDA is an increase in EDSS as compared to baseline according to the criteria above which is confirmed at a scheduled visit after 12 weeks. The increase needs to be persistent at all EDSS assessments (scheduled or unscheduled) between onset (first EDSS increase in the considered period) and confirmation. 12-week CDA is assessed sequentially up to the last available EDSS assessment for a subject in the study following the algorithm detailed below.

Disability progression can only be confirmed at a scheduled visit, where the EOT (Up to Week 156 or earlier or premature EOT visit), and FU visits count as scheduled visits, outside of an ongoing relapse. In this context, relapse duration is defined as period between start date (inclusive) and end date (exclusive) if available and limited to 90 days from onset if end date is not available or duration is longer than 90 days.

Algorithm for deriving 12-week CDA

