7.1.2 Full analysis set

The full analysis set (FAS) includes all randomized subjects who were treated with at least one dose of study treatment and have at least one post-baseline efficacy assessment.

- In order to preserve the randomization, subjects will be evaluated according to the treatment they have been randomized to (which may be different to the treatment they have received) and stratum information used for randomization as recorded in the IVRS system (which may be different to the information available on the eCRF after data validation);
- Unless otherwise stated, all available efficacy data for the primary and secondary endpoints up to the EOS visit [see Section 11.4] will be included in the analysis, regardless of study treatment discontinuation and/or switches to alternative MS treatments.

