11 GENERAL DEFINITIONS AND DERIVATIONS

11.1 Dates, times and days

Study treatment start date see definition in Section 5.3.1.1.

End-of-Treatment (EOT) / Study treatment end date, defined as the latest study treatment end date as recorded on the Study Drug Log eCRFs [see Section 5.3.1.1].

End-of-Study (EOS) date is defined as the 'Date of Subject Decision' (if reason for study discontinuation was 'Subject Decision'), 'Date of Physician Decision' (if reason for study discontinuation was 'Physician Decision') collected on the 'Study Discontinuation' eCRF, or 'Date of recorded last study visit / assessment' (if reason for study discontinuation was 'Sponsor Decision'), unless a subject is lost to follow-up or dies, in which case 'Date of last successful contact' from the Study Discontinuation eCRF or 'Date of Death' from Death eCRF are used. If missing, the last recorded visit date (i.e., the latest assessment date within any visit) is considered as the EOS date [see Section 5.1.6].

Screening date defined as the visit date of the last available screening visit, i.e., date of Visit 1A for re-screened subjects, date of Visit 1 for all others.

Study Day refers to the number of days elapsed since randomization date plus 1 (e.g., Study Day 1 is the day of randomization). For dates prior to randomization, study day is the negative number of days elapsed between the date under consideration and the day of randomization. Therefore, the study day is always different from 0.

For efficacy analyses also referred to as 'Day'.

Treatment Day refers to the number of days elapsed since study treatment start date plus 1 (e.g., Treatment Day 1 is the day of study treatment start). For dates prior to study treatment start, treatment day is the negative number of days elapsed between the date under consideration and the day of study treatment start. Therefore, it is always different from 0.

For safety analyses also referred to as 'Day'.

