11.2 Analysis period definitions

11.2.1 Efficacy study periods

The ‘Efficacy Study Period’ of primary interest in this study is the period from randomization up to the EOS date, defined as: [Randomization; EOS].

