Premature EOT visits are mapped to and summarized within a scheduled visit following the window approach described in Section 11.3; they will not be summarized as “Visit 18 - Week 156” unless they are mapped to this visit as per approach described in Section 11.3.

As per protocol, total lymphocyte counts will be assessed every 4 weeks up to Week 24 (i.e., there are 3 protocol mandated between-visit assessments for those tests at Week 8, Week 16, and Week 20 when no regular visit is scheduled).

These assessments are considered scheduled and are included in corresponding by-visit tabulations labeled as follows:

- Additional Visit - Week 8
- Additional Visit - Week 16
- Additional Visit - Week 20

Visit-based efficacy are summarized according to the nominal visit up to EOS, irrespective if conducted during PTOP or not:

- Baseline (Derived)
- Visit 4 - Week 2
- Visit 6 - Week 12
- Visit 7 - Week 24
- Visit 9 - Week 48
- Visit 11 - Week 72
- Visit 13 - Week 96

- Visit 15 - Week 120
- Visit 17 - Week 144
- Visit 18 - Week 156

Premature EOT visits are mapped to and summarized within a scheduled visit following the window approach described in Section 11.3; they will not be summarized as “Visit 18 - Week 156” unless they are mapped to this visit as per approach described in Section 11.3.

EOS visit is defined for efficacy endpoints and JCV:

- For subjects who complete the treatment period, and for subjects who prematurely discontinue study treatment and do not enter the PTOp, the EOS visit corresponds to the 30 day follow-up visit (FU) for efficacy endpoints, and for the last available visit for JCV.
- For subjects who prematurely discontinue study treatment and enter the PTOp period, the EOS visit corresponds to the last visit of the PTOp.

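### Two end-of-study rules conflict for subjects who attend EOT or FU after deciding to leave: the EOT MRI may be in or out of CUAL/T2, and relapse follow-up time stops while relapses still count

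*SAP*

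**What the plan says.** **Date rule.** For a subject's own decision or withdrawal of consent, SAP 5.1.6 states: "The EOS date is defined as the ‘Date of Subject Decision". Section 11.1 does the same for the physician: "Date of Physician Decision' (if reason for study discontinuation was 'Physician Decision') collected on the 'Study Discontinuation' eCRF". For a sponsor decision, and whenever the date is missing, 5.1.6 uses the last recorded visit or assessment. The efficacy period in 11.2.1 "is the period from randomization up to the EOS date, defined as: [Randomization; EOS".

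**Visit rule.** Section 7.1.2 includes "all available efficacy data for the primary and secondary endpoints up to the EOS visit" and refers to 11.4. There, for subjects who stop treatment early and do not enter the PTOP, "the EOS visit corresponds to the 30 day follow-up visit (FU) for efficacy endpoints". For those who enter the PTOP it is the last PTOP visit. Section 2.1.1 agrees.

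**Endpoints.**
- CUAL (5.4.2.3) and new or enlarging T2 lesions (5.4.3.3) are summed over MRI visits up to EOS, without saying whether date or visit is meant. Their offset is time to the last MRI included.
- The ARR offset (5.4.1), time in study (5.1.7) and censoring of time to first relapse (5.4.2.2) use the EOS date.
- 5.4.1 first names the EOS date as the end of the relapse count. Its last sentence then takes this to mean every confirmed relapse that did not start before randomization.
- 5.4.2.1 says CDA runs up to EOS, and also: "12-week CDA is assessed sequentially up to the last available EDSS assessment for a subject in the study".

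**The concern.** Visits after a decision to leave are foreseen. Section 2.1.1 puts all subjects into at least 30 days of safety follow-up after the last dose. Table 3 schedules EDSS at EOT and FU and MRI at EOT, and 5.4.2.3 adds an MRI at a premature EOT visit. A subject can therefore have efficacy data dated after the EOS date but at or before the EOS visit. Two programmers following different sections would build different CUAL and T2 datasets.

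The relapse endpoints have a related fault: events are open-ended while time at risk stops at the decision. The rule also depends on why the subject left. A subject stopped by the sponsor is followed to the last visit, whereas one leaving by subject or physician decision is not. Lack of efficacy is a listed sub-reason for both of those decisions, so such exits may be related to outcome. With 136 subjects randomized, a few records can matter, and 9.6.3 plans no sensitivity analysis that would show the effect.

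**Working it through.** The SAP gives no figure for this point, so there is nothing to reproduce. The rules are applied to hypothetical subjects.

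**Inputs**
- EOT visit: window +7 days. FU visit: last dose +30 days, window +7 (Table 3).
- ARR observation time: (EOS date − randomization date + 1)/365.25 (5.4.1).
- CUAL/T2 offset: (last MRI date − randomization date + 1)/365.25 (5.4.2.3, 5.4.3.3).
- CDA confirmation: at least 70 days after onset; EOT and FU count as scheduled visits (5.4.2.1).
- Assumption: the study-exit decision is dated on the last-dose day and the subject still attends EOT and FU. Days are study days.

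**1. Gap between EOS date and visit**
- EOT, with its MRI: 0 to 7 days; 7/365.25 = 0.019 years.
- FU: 30 to 37 days; 30/365.25 = 0.082 and 37/365.25 = 0.101 years, i.e. 8-10% of a year.

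**2. CUAL/T2.** Decision on day 120, before Week 24; EOT MRI on day 127.
- Visit rule: the scan counts, with offset 127/365.25 = 0.348 years.
- Date rule: the scan is out. Unless an unscheduled scan exists, the subject has no post-baseline MRI.

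**3. ARR.** Decision on day 125; confirmed relapse on day 140; FU on day 155-162. By the last sentence of 5.4.1 the relapse counts.
- Time to the decision: 1/(125/365.25) = 2.92 per year.
- Time to FU: 1/(155/365.25) = 2.36, or 1/(162/365.25) = 2.25 per year.

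These are one subject's raw rates, not effects on the model estimate. A similar subject without a relapse contributes zero events over 125 days instead of 155-162.

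**4. Time to first relapse.** The subject in step 3 has an event on day 140. The one without a relapse, observed equally long, is censored on day 125. The time after the decision is used only if a relapse occurs.

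**5. CDA.** EDSS increase on day 85; decision on day 125; FU on day 155-162.
- FU is 155 − 85 = 70 to 162 − 85 = 77 days after onset, so it can confirm.
- A strict date cut ends 125 − 85 = 40 days after onset, so there is no confirmation.
- The 5.4.2.1 algorithm takes all post-baseline EDSS assessments and censors at the last one without an increase, not at EOS. Followed as written, it includes FU.

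**The case against.** The decision date comes from the Study Discontinuation form; stopping drug is recorded separately (5.1.5). A subject who stops drug for lack of efficacy should complete EOT and FU and then enter the PTOP (2.1.1). If that subject leaves the study later, EOT and FU precede the EOS date and nothing is in dispute. Subjects still on drug at termination attend EOT and FU (section 2), and if they exit by sponsor decision their EOS date is the last visit or assessment. Withdrawal of consent may mean that no later visits exist. All this stands, and it limits the problem to subjects whose recorded exit decision precedes an attended EOT or FU visit.

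A reader might infer more, in four ways that the SAP does not support:
- **That everyone leaving by subject or physician decision is affected.** Assuming 10-20% of 136 gives about 14-27 subjects, but the share is not in the SAP and the result is a ceiling. It removes nobody whose visits came before the decision or who had none after it.
- **That the MRI gap is 30-37 days.** MRI is scheduled at EOT, not FU, so under the stated assumption the gap is 0-7 days. If the decision is recorded at the EOT visit, no scan is in dispute.
- **That CDA loses its confirming assessments.** The algorithm in 5.4.2.1 largely settles this in favour of inclusion.
- **That CUAL/T2 observation time is cut at the EOS date.** Its offset runs to the last MRI included. The open question is whether a scan is included.

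The stakes are also modest: the secondary endpoints are exploratory (9.7), CDA has only Kaplan-Meier summaries (9.7.1), and the report is synoptic. None of this says which rule governs CUAL/T2, or explains why relapses and their time at risk end at different points. The ARR model is the analysis retained for formal testing.

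**Conclusion.** The contradiction is real and unresolved in the SAP, but narrow. It can remove an EOT scan from CUAL and T2, and in the extreme a subject's only post-baseline scan. It also shortens the ARR offset, time in study and first-relapse censoring time by 30-37 days per affected subject, assuming the decision falls on the last-dose day and FU is attended. A decision recorded later gives a smaller gap. For CDA, only the phrase about EOS needs aligning with the algorithm.

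The number affected is not given and is probably small. Bias between arms is not demonstrated; it arises only if such exits differ by arm. The point should be corrected because the result depends on which section is programmed, and because counting events without their time at risk is wrong whatever the number.

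**What to change.** - In 5.1.6 and 11.1, define the EOS date for subject or physician decision as the later of the decision date and the last recorded study visit or assessment, subject to any limits on data use after withdrawal of consent. This extends the last-visit approach that 5.1.6 already applies to sponsor decision and missing dates.
- Use this single date as the cut-off for relapse counts, ARR offset, censoring, EDSS and MRI in 5.1.7, 5.4, 7.1.2 and 11.2.1. In 7.1.2, replace the EOS visit with the EOS date. In 5.4.1, apply the cut to the relapse count explicitly. In 5.4.2.1, align the EOS phrase with the last available EDSS.

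The cost is SAP wording and a small change to the EOS derivation. Observation time becomes slightly longer for the affected subjects, including in the primary offset, so the change should be made before unblinding. Membership of the post-treatment safety set (7.1.4.1), which requires an EOS date more than 15 days after EOT, may also change: a subject who decides on the last-dose day but attends FU is now excluded and would then be included.
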